11.2.2. Recording and Reporting AEs

All AEs and SAEs will be collected from the signing of the informed consent form (ICF) until the exit visit.

SAEs will be followed until satisfactory resolution, until baseline level is reached, or until the SAE is considered by the investigator to be chronic or the patient is stable, as appropriate.

All SAEs that are suspected of being related to study treatment must be reported immediately to the sponsor if the investigator becomes aware of them, regardless of the time since the completion of the clinical trial.

Any events that occur prior to the start of dosing will be categorized as pretreatment events; events occurring after the start of dosing and up to 56 days beyond the last dose of study medication will be recorded as TEAEs.

For each AE, the investigator will evaluate and report the onset date (and time, if applicable), resolution date (and time, if applicable), intensity, causality, action taken, seriousness criteria met (if applicable), and whether or not the participant discontinued the study as a result of the event. AEs characterized as intermittent require documentation of the start and stop of each incidence. If possible, the outcome of any AE resulting in permanent discontinuation or that was present at the end of the study should be reported. AEs resulting in interruption or discontinuation of study drug or that are present at the exit visit should receive follow-up as appropriate.

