7.1. Adverse Events

Treatment-emergent adverse events (TEAEs) are defined as those AEs that develop or worsen after the first dose of double-blinded investigational product and up to 56 days beyond the last dose of investigational product. Analysis of AEs (as discussed below) will be limited to TEAEs, but data listings will include all AEs regardless of their timing.

All reported AEs will be coded using the current version of MedDRA and summarized by System Organ Class (SOC) and Preferred Term (PT). All summaries by SOC and PT will be ordered by decreasing frequency of participants within each SOC and then similarly by decreasing frequency of participants within each PT based on the pegcetacoplan group. In the case of equal frequency of number of participants in SOCs or PTs, summaries of TEAEs will be sorted alphabetically. Rules for handling missing severity, relationship to study drug, relationship to infusion procedure, outcome, and missing dates of AEs are described in Section 13.

If a PT was reported more than once for the same participant, that participant would only be counted once in the incidence for that PT. For participants experiencing the same PT at multiple severities, the occurrence of the AEs with the greatest severity will be used in the analysis of incidence by severity. For participants experiencing the same PT at multiple relationship levels, the occurrence of the AEs with the strongest relationship to study drug will be used in the analysis of incidence by relationship to study drug.

The AE summaries will be presented by treatment group. In addition, the incidence of death, stratified by transplant history will be summarized.

In post-transplant participants, the number and incidence of rejection episodes at week 26 will be tabulated by treatment group. Additionally, if the number of participants is sufficient, the results for treatment groups will be compared using Fisher's exact test (or a stratified Cochran-Mantel-Haenszel χ -square test as appropriate).

In participants who are posttransplant, the number and incidence of graft loss at week 26 will be tabulated by treatment group. Additionally, if the number of participants is sufficient, the results for treatment groups will be compared using Fisher's exact test (or a stratified Cochran-Mantel-Haenszel γ -square test as appropriate).

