Pre-existing ADA will be defined as follows: any participant with an ADA positive baseline sample from the total participants with a baseline sample result.

Evaluable participants will be defined as follows: a participant with at least one sample taken with a reportable result after first dosing during the treatment or follow-up period.

Evaluable participants will be classified as follows for ADA response:

- ADA-Positive Participant An evaluable participant with at least one pre-dose sample and one treatment-emergent or treatment-boosted ADA-positive sample at any time after dosing
- ADA-Negative Participant An evaluable participant without a treatment-emergent or treatment-boosted ADA-positive sample during the treatment or follow-up period
- ADA-Inconclusive Participant An evaluable participant who cannot be classified as either ADA-positive or ADA-negative (eg, assay drug tolerance issues, post-dose positive without a baseline sample, positive baseline and positive post-dose sample without a titer value, etc.)

ADA positive responses will be classified as follows:

- Treatment-Boosted ADA Response An evaluable participant with a baseline ADA positive sample and a post-dose ADA positive sample that is $\geq 4x$ the baseline titer (eg, baseline titer of 10 vs. post-dose titer of 40)
- Treatment-Emergent ADA Response An evaluable participant with a baseline ADA negative sample and an ADA positive sample after treatment, ADA developed *de novo*

The kinetics of ADA positive responses will be classified as follows:

- Transient ADA Response
 - Treatment-emergent positive participants are classified as having a transient response if they have only a single ADA positive sample (that was not the last assessment), or more than 1 ADA positive sample where the first and last ADA positive samples are separated by a period of less than 112 days (16 weeks), irrespective of any negative and positive samples in between.
 - Treatment-boosted ADA positive participants are classified as having a transient response if they have only a single ADA boosted sample (that was not the last assessment), or more than 1 positive boosted sample where the first and last ADA positive samples are separated by a period of less than 112 days (16 weeks), irrespective of any negative and positive samples in between.
- Persistent ADA Response

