1. INTRODUCTION

This statistical analysis plan (SAP) addendum provides a technical and detailed elaboration of the statistical analyses of efficacy and safety, supplementing what is described in the main SAP of the primary analysis (Week 26) and overall (combined with Week 26 SAP) clinical study report (CSR). The specified analyses to be performed as part of this SAP addendum do not supersede or replace any previously specified analyses, unless specified otherwise.

The specified analyses in this SAP addendum will serve the purposes of the planned analyses for the open-label period (OLP) reporting once all participants have completed the open-label treatment period or discontinued early and all corresponding data have been entered into the database, reviewed, cleaned, and finalized, and the database is locked.

The analyses of the OLP data associated with the primary CSR (dated 05 December 2024) were described in Version 1.0 of the SAP Addendum.

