7. SAFETY ANALYSIS

7.1. Adverse Events

Further detail is provided in the main SAP Section 7.1. The same summaries for RCP as in the main SAP will be repeated for OLP (except for rejection episodes and graft loss where only descriptive summaries are required at Week 52) using all available data through the Week 52 assessment.

Besides the AESI summaries as per the CRF form checkbox question "Is this event an AESI?", additional summaries for the AEs of special search will be provided based on the special search teams provided by Apellis safety team, more specifically:

- Infections: SOC-infections and infestations; HLGT- Bacterial infectious disorders, HLGT- Fungal infectious disorders, HLGT- Viral infectious disorders
- Hypersensitivity: SMQ-Hypersensitivity (narrow)
- Acute Kidney Injury: SMQ- Acute Renal Failure (narrow)
- Thrombocytopenia: HLT- Thrombocytopenias, PT-Platelet count decreased, PT-Plateletcrit decreased, PT-Platelet count abnormal

AEs will be summarized by treatment groups and period. Data will be presented in 5 columns: (1) Pegcetacoplan group's RCP results; (2) Pegcetacoplan group's OLP results; (3) Placebo group's OLP results; (4) OLP results combined (in other words, combining columns 2 and 3); (5) for all results since Pegcetacoplan injection (in other words, combining columns 1 and 4). The classification of AEs in the RCP or OLP will be based on the AE start date compared to the RCP/OLP threshold as defined in the main SAP Section 13.3.

For AE summaries that relate to rejection episodes, in addition to the preferred terms specified in the main SAP, one additional preferred term of "Transplant rejection" is also added based on Apellis team review.

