10. IMMUNOGENICITY

Refer to main SAP Section 10 for further details of the analysis.

The same summaries for RCP as in the main SAP will be repeated using all available data through the Week 52 assessment.

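### The final SAP addendum stops its safety summaries at week 52, while the plan's own TEAE window and person-time run to 56 days after the last dose

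*SAP*

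**What the plan says.** Protocol 11.2.2 sets the collection period: "All AEs and SAEs will be collected from the signing of the informed consent form (ICF) until the exit visit". It also sets the treatment-emergent window: "events occurring after the start of dosing and up to 56 days beyond the last dose of study medication will be recorded as TEAEs". Main SAP 7.1 keeps that tail, counting AEs that start or worsen after the first dose "and up to 56 days beyond the last dose of investigational product".

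Under Protocol 6.1.4, participants who do not enter the extension study stop pegcetacoplan and complete an 8-week follow-up period. Protocol Table 2 schedules AEs, vital signs, hematology, chemistry, PK and serum complement at weeks 54, 56 and 60. ECG, plasma complement and ADA are scheduled at weeks 54 and 60.

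Main SAP section 1 covers the randomized controlled period (RCP) only and leaves later data to an addendum. Addendum v2.0 (10 February 2025) is the version for the final database lock:

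- Section 7.1 repeats the AE summaries for the open-label period (OLP) and ends the data where the parenthesis closes: "are required at Week 52) using all available data through the Week 52 assessment".
- Sections 7.2 to 7.4 apply the same limit to by-visit laboratory, vital sign and ECG summaries. Sections 8 and 9 apply it to PK and PD.
- Section 10 says of the immunogenicity summaries that they will be "repeated using all available data through the Week 52 assessment".
- The AE tables have five columns, all built from the RCP and the OLP. None is for follow-up.
- Section 1 places the analysis "once all participants have completed the open-label treatment period or discontinued early", without mentioning the end of follow-up.

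The main SAP elsewhere expects follow-up data. Its Table 5 has windows for weeks 54, 56 and 60, and its section 10 calls a participant evaluable for ADA on the basis of a "reportable result after first dosing during the treatment or follow-up period".

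**The concern.** The plan defines an event 40 days after the last dose as treatment-emergent, has sites record it, and then sets a data limit that keeps it out of the incidence tables if it falls after week 52. Only the addendum could summarize follow-up: the main SAP stops at the RCP, and Addendum v1.0, which is not among the documents, is described as covering interim data at the week 26 cut.

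At stake is the reporting of what happens in the 8 weeks after pegcetacoplan is stopped at the end of the study, and of the last ADA samples. There is also an internal error. The exposure-adjusted rates use the 56-day tail in the denominator, while the week 52 limit removes it from the numerator. Addendum section 15 lists its departures from the protocol and main SAP, and this limit is not among them.

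**Working it through.** **1. The plan's own figure.** Protocol Table 2 puts week 52 on day 364 and the week 60 exit visit on day 420. 420 − 364 = 56 days = 8 × 7. The TEAE tail therefore matches the scheduled follow-up period exactly for someone whose last dose is on day 364.

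**2. How much of the tail lies beyond the cut.** With last dose on study day L and the week 52 assessment on its nominal day, days lost = max(0, L + 56 − 364).

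| Last dose (day) | Days of the 56-day window after day 364 |
|---|---|
| 308 (week 44) | 0 |
| 322 | 14 |
| 336 | 28 |
| 350 | 42 |
| 364 | 56 |

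A participant who stops by day 308 loses nothing. A day-364 completer who does not roll over loses all of it, with visits 17, 18 and 19.

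**3. ADA samples.** Protocol Table 2 schedules ADA at weeks 1, 4, 16, 24, 36, 52, 54 and 60. Two of the eight fall after the cut. Evaluability is hardly affected, since one reportable post-dose sample is enough. Classification can be: a first positive at week 54 or 60 would not be counted, and main SAP 10 separates transient from persistent responses by the spacing of positives and the status of the last sample.

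**4. Exposure-adjusted rates.** Main SAP 7.1 gives the rate as n × 100/EY, with n the participants affected and EY the summed time to onset divided by 365.25. Without an event, the time is (last dose date + 56 days) − Day 1 date + 1. For last dose on day 364:

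- credited time = (364 + 56) − 1 + 1 = 420 days;
- time in which an event can be counted under Addendum 7.1 = 364 days;
- share that cannot contribute an event = 56/420 = 13.3%;
- for a rare event among such participants, the rate is about 364/420 = 0.867 of the rate with matched dates.

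The formula makes no exception for participants who enter the extension study, so read literally it credits them with the same 56 days.

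The addendum does not say whether the clock restarts for OLP columns. If it restarted on day 182, the time to day 364 would be 364 − 182 + 1 = 183 days and the share 56/(183 + 56) = 23.4%. From day 196 it would be 169 days and 56/(169 + 56) = 24.9%. These two figures rest on that assumption.

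**The case against.** The strongest reply is that a TEAE definition and a reporting cutoff are different things, and that week 52 fits the stated objective of safety over 52 weeks of treatment. Addendum section 1 leaves earlier specifications in force unless it says otherwise, so the 56-day definition carries over. Main SAP 13.3 gives the OLP a start but no end, so a programmer could count a week 55 event under OLP. That reading is possible, but it conflicts with the explicit limit in Addendum 7.1. Two readings that give different tables are themselves a reason to amend.

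Other parts of the reply stand and limit the point. A reader might infer that all off-drug follow-up goes unsummarized. The documents do not support that:

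- Under Protocol 7.3.1, participants who stop during the OLP enter follow-up when they stop. Main SAP 13.4 maps follow-up visits to scheduled visits. Their data before week 52 are kept.
- Main SAP 13.5, carried over by Addendum section 13, uses all post-baseline assessments to determine potentially clinically significant (PCS) values. Those tables may already include follow-up.
- Main SAP 7.1 lists all AEs whatever their timing, although a listing gives no incidence.

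A reader might also infer that participants who do not roll over tolerated the drug poorly, or that the follow-up ADA samples are the only conclusive ones. Neither is shown. Rollover rests on the investigator's view of benefit, and those with poor tolerability may stop earlier, where the cut has less effect. The documents give no pegcetacoplan concentrations to set against the ADA interference thresholds.

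**Conclusion.** The point holds for participants whose 56-day window extends past week 52, mainly completers who do not roll over. As written, the addendum drops events that the plan itself defines as treatment-emergent from the incidence tables, and drops weeks 54 to 60 from the by-visit and ADA summaries. Per participant the loss runs from 0 days (last dose by day 308) to 56 days (last dose on day 364).

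The mismatch in the exposure-adjusted rates is 13.3% of credited time for an event-free day-364 completer. It assumes that the week 52 assessment falls on its nominal day and that the clock starts at Day 1. The effect on a study-level rate cannot be computed, because the numbers of non-rollovers and of early stoppers are not given. The primary efficacy analysis is unaffected. The matter should be corrected before the final tables are produced.

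**What to change.** 1. In Addendum 7.1, summarize TEAEs through last dose + 56 days, with a separate column or row for onset in post-treatment follow-up. Tie the limit to the last dose rather than to the exit visit, whose ±7-day window could admit events beyond 56 days.
2. In Addendum 7.2 to 7.4 and 8 to 10, add weeks 54, 56 and 60 where each assessment is scheduled, using main SAP Table 5 and, for assessments outside that table, the adjusted windows allowed by main SAP 13.4. Include follow-up samples in the ADA classification.
3. In the exposure-adjusted rates, end person-time on the date to which events are counted, including for participants who enter the extension study. State when the clock starts for the OLP columns.
4. Define the end of the OLP, and confirm that the final lock follows the last exit visit.

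The cost is SAP wording and table programming on data already collected. If the lock is now planned earlier, it would wait up to 8 weeks for the last participant who does not roll over.

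If the sponsor keeps the week 52 cut, Addendum section 15 should state it, and person-time should be censored at that cut.

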13.3. Definition of Baseline, RCP, and OLP

For all evaluations unless otherwise noted, baseline is defined as the most recent non-missing measurement prior to the first administration of study drug. Baseline can be the same date as first dose, given the measurement is expected prior to first dose when only date information is available.

In by-visit summary tables, the baseline will be summarized using all available data, but also for each visit using only the baseline data from participants with available data at the visit; hence the mean change from baseline will equal the mean visit value – mean baseline value.

Throughout this document 'change from baseline' refers to the actual change from baseline (ie, visit value – baseline value).

The date when a participant receives first administration of OLP drug will be defined as the start date of the participant's OLP, and that date minus one day will be the end date of the participant's RCP.

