13.6.2.1.2. Missing Day and Month

- If the year of the incomplete start date is the same as the year of the date of the first dose of investigational product, then the day and month of the date of the first dose of investigational product will be assigned to the missing fields.
- If the year of the incomplete start date is before the year of the date of the first dose of investigational product, then December 31 will be assigned to the missing fields.
- If the year of the incomplete start date is after the year of the date of the first dose of investigational product, then 01 January will be assigned to the missing fields.

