13.6.2.1.4. Missing Day Only

- If the month and year of the incomplete start date are the same as the month and year of the date of the first dose of investigational product, then the day of the date of the first dose of investigational product will be assigned to the missing day
- If either the year is before the year of the date of the first dose of investigational product or if both years are the same but the month is before the month of the date of the first dose of investigational product, then the last day of the month will be assigned to the missing day
- If either the year is after the year of the date of the first dose of investigational product or if both years are the same but the month is after the month of the date of the first dose of investigational product, then the first day of the month will be assigned to the missing day.

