13.6.3. Missing Date Information for Adverse Events

For AEs with partial start dates, non-missing date parts will be used to determine if the AE is treatment-emergent or not. If a determination cannot be made using the non-missing date parts as to when the AE occurred relative to study drug administration, eg, AE start year and month are the same as the year and month of the first dose of investigational product, then the AE will be classified as treatment-emergent.

To facilitate categorization of AEs as treatment emergent, imputation of dates can be used. For AEs, the default is to only impute incomplete (ie, partially missing) start dates. Incomplete stop dates may also be imputed when calculation of the duration of an AE is required per the protocol. If imputation of an incomplete stop date is required, and both the start date and the stop date are incomplete for a participant, impute the start date first.

- Rules to impute incomplete start date are the same as stated in Section 13.6.2.1.
- Rules to impute incomplete stop date are the same as stated in Section 13.6.2.2.

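### For placebo participants who switch to open-label pegcetacoplan, adverse events with a partial start date default to the placebo period and leave the on-drug columns of the addendum tables

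*SAP*

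**What the plan says.** - **Period.** SAP Addendum 7.1: "The classification of AEs in the RCP or OLP will be based on the AE start date compared to the RCP/OLP threshold". Main SAP 13.3 sets that threshold: "The date when a participant receives first administration of OLP drug will be defined as the start date of the participant's OLP". The randomized period ends the day before.
- **Columns.** Addendum 7.1 lists five: pegcetacoplan group RCP, pegcetacoplan group OLP, placebo group OLP, both OLPs combined, and a fifth "for all results since Pegcetacoplan injection (in other words, combining columns 1 and 4". None holds the placebo group's RCP.
- **Partial start dates.** Main SAP 13.6.3: "Rules to impute incomplete start date are the same as stated in Section 13.6.2.1". Those are the medication-date rules. With only the day missing, in a month later than the first-dose month, "then the first day of the month will be assigned to the missing day" (13.6.2.1.4). With day and month missing, in the first-dose year, "then the day and month of the date of the first dose of investigational product will be assigned to the missing fields" (13.6.2.1.2). In a later year the date becomes 1 January.
- **Treatment emergence.** Main SAP 7.1 counts "AEs that develop or worsen after the first dose of double-blinded investigational product". Section 13.6.3 classes an event of undeterminable timing as treatment-emergent, but does not mention the period.
- **Anchor.** Protocol 9.2.2 counts placebo as investigational product, so a placebo participant's first dose is Day 1.

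**The concern.** A placebo participant has two first doses that matter for safety: Day 1, and the first pegcetacoplan dose about six months later. The date rules recognise only Day 1. At the switch, a partial start date is resolved towards the placebo period, so the event leaves columns 3, 4 and 5. Elsewhere the SAP resolves doubt the other way: unclear timing is treatment-emergent (13.6.3), missing severity on treatment becomes severe (13.6.4) and missing causality becomes related (13.6.5).

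At stake is the account of early exposure in participants meeting pegcetacoplan for the first time, including infection and hypersensitivity, for which Addendum 7.1 adds dedicated searches. With 124 participants enrolled and 1:1 allocation there are at most about 62 switchers (124/2, assuming equal arms and that all switched), so single events can matter.

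A related gap is that no rule says where to count an event that begins on placebo and worsens on open-label drug.

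**Working it through.** The plan gives no figure on this point. The check applies its date rules to a calendar.

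**Inputs.** Day 1 on each of 730 dates (2022-2023). Open-label start on study day 182 or 196, the week 26 and week 28 visits in the schedule of activities. True onset on each of the 182 days of the 26-week open-label period. Uniform onset is an assumption.

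**1. Which branch applies.** The switch month equalled the first-dose month for 0 of the 730 Day 1 dates. The later-month branch therefore always applies, and a missing day becomes the 1st.

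**2. Complete dates.** None is misassigned. A fully dated on-drug onset reaches columns 3, 4 and 5.

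**3. Day missing, true onset on drug in the switch month.** An event is misplaced if the 1st precedes the first open-label dose.
- Start on day 182: 10,773 of 11,504 = 93.6%.
- Start on day 196: 10,756 of 11,487 = 93.6%.
- Hand check for a 30-day month: a switch on day d leaves 31 − d on-drug days. These sum to 465, and only the 30 belonging to d = 1 are kept, so (465 − 30)/465 = 93.5%.

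**4. Day missing, true onset anywhere in the open-label period.** Only the switch month is affected. Misplaced days per participant: 10,773/730 = 14.76. Share: 14.76/182 = 8.1%.

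**5. Only the year known.** The event is kept only if its year is later than the year of the switch, apart from a switch on 1 January. For a switch date uniform over the year, the expected share of the 182 days falling in the next year is 182/(2 × 365) = 24.9%, so about 75.1% are misplaced. The enumeration gives 74.9%.

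**6. Direction.** With a missing day, none of the 10,745 true placebo-period days in the switch month (10,761 for the later start) moves to the open-label period. The error runs one way.

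**7. Example.** Day 1 is 10 January 2023 and open-label start is 24 July 2023 (day 196). An event on 29 July recorded as July 2023 is imputed to 1 July and classed as placebo RCP. Recorded as 2023 only, it is imputed to 10 January, with the same result.

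**8. Overall size.** The share of partial dates is not given. If 1-3% of events lacked the day (an assumption), the loss would be 0.01 × 8.1% = 0.08% to 0.03 × 8.1% = 0.24% of switchers' open-label events, about 1 to 2 per 1,000.

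**The case against.** **Imputation may not decide the period.** Section 13.6.3 uses the known date parts first and allows imputation as a help in judging treatment emergence. Neither it nor the addendum says that an imputed date settles RCP versus OLP. That is fair. But the addendum needs a start date to compare with the threshold, its Section 13 points back to main SAP Section 13, and no other rule for partial start dates exists. If imputation is not meant to apply, the event has no defined period, which the same sentence would repair.

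**The events are reported elsewhere.** This stands. Main SAP 7.1 tabulates randomized-period events by treatment group and lists all adverse events whatever their timing, and Addendum Section 1 says it does not replace earlier analyses unless specified. A reader might infer that the events vanish from reporting, but they are absent only from the five-column addendum tables. If counted as placebo events under the main SAP, they would tilt that comparison slightly towards pegcetacoplan.

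**Most on-drug events are safe.** This also stands. A reader might infer that events occurring on pegcetacoplan in switchers generally drop out, but a complete start date is always placed correctly. In the pegcetacoplan group an event may move between columns 1 and 2 but stays in column 5.

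**Worsening depends on recording.** A reader might infer that every event worsening after the switch is lost. The documents do not show that. A new record would carry its own start date and fall in the OLP. An updated record would stay in the placebo period. Protocol 11.2.2 asks for onset, resolution and intensity, and for a start and stop for each incidence of an intermittent event. It does not say whether worsening of an ongoing event opens a new record, and names no date for a severity change.

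**Dates near the switch should be well captured.** Adverse events are reviewed at weeks 24, 26 and 28, each within 3 days, open-label dosing starts at a visit, and events of special interest are reported within 24 hours. This makes partial dates less likely, but the documents do not exclude them.

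**Conclusion.** The point holds for partial start dates in placebo switchers. Read as written, the rules send about 93-94% of day-missing on-drug onsets in the switch month, about 8% of day-missing onsets over the open-label period, and about 75% of year-only onsets to the placebo RCP, outside columns 3, 4 and 5. These shares assume uniform onset, and that the first dose of investigational product means Day 1. If it meant the first pegcetacoplan dose, the same-month branch would place day-missing switch-month events in the OLP. Protocol 9.2.2 and the reference to double-blinded product in main SAP 7.1 support the Day 1 reading.

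The absolute number cannot be computed and is probably small, and Addendum 6.2 plans no formal testing of open-label data. The case for a change is that the error is one-directional, runs against the SAP's own cautious defaults, and falls at first exposure. For worsening, only the missing rule is established, not a loss of events.

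**What to change.** Add two statements to Addendum 7.1:

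1. If the non-missing date parts do not place an event's start clearly before the first open-label dose, the event is assigned to the open-label period.
2. An event ongoing at the switch with a recorded increase in severity or seriousness on or after the first open-label dose counts as an open-label event, where the recorded data date that worsening.

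The first costs one sentence and a small programming change. The second depends on whether the case report form dates a change in severity or opens a new record; that should be confirmed before the sentence is adopted.

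The downside is that some true placebo-period events will be counted on drug. Under uniform onset, about 10,745/(10,745 + 11,504) = 48% of day-missing events in the switch month began before the switch, and all would move unless other date information places them earlier. That is the same conservative trade that 13.6.3 accepts at Day 1. If outputs already exist, a sensitivity table under the revised rule, with the number of partial dates in each period, is enough.
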